## **LIST OF ABBREVIATIONS**

ARC	Clinical Research Associate (monitor)
GCP	Good Clinical Practice
PPC	Committee for the Protection of Individuals
CNIL	Commission Nationale de l'Informatique et des Libertés
eCRF	Electronic Case Report Form
ICH	International Conference on Harmonization
MR	CNIL Reference Methodology
RIRCM	Minimal Risk and Minimal Constraint Intervention Research

## **1. RATIONALE FOR THE STUDY**

### ***1.1. POSITIONING OF THE RESEARCH***

Echo guided hand infiltration is usually prescribed to relieve chronic pain. According to *the International Association for the Study Pain*, pain is "an unpleasant sensory and emotional experience associated with actual or potential tissue damage, or described in terms suggestive of such damage [1]".

Echo guided infiltration is a relatively common procedure and is generally considered to be locally painful. This pain induced by the treatment, leads to a strong apprehension among patients who have to undergo this procedure.

In order to reduce the stress of the patients, several approaches were put in place, namely: explanation of the procedure, setting up a relaxed atmosphere (notably through discussion). All these elements constitute a form of hypnosis known as conversational. Nevertheless, according to our observations, it remains insufficient for the management of the pain of infiltration.

The practice of hypnosis to improve patient comfort during care has gradually appeared in hospital departments. It is used in surgery, particularly for dressings for burn victims, and increasingly in medicine [2]. Jean-Marc Benhaim, in 2003, indicated that "therapeutic hypnosis is a relational experience bringing into play physiological and psychological mechanisms allowing the individual to better live, to attenuate or to eliminate an acute or chronic painful pathology [3]. The hypnotic state would allow to modulate feelings, in particular emotions such as pain or anxiety [4 & 5].

There are several forms of hypnosis, Ericksonian hypnosis lets the subject solve his problem without direct intervention dictating the solution. It is only necessary to guide him, to choose the ideas, the images... that he likes and that suit him.

This decreases attention, the relationship to reality, spontaneous mental activity and the perception of time, but allows the refocusing of attention towards bodily sensations and mental contents proposed by the induction, as well as concentration and adherence to the imagery.

Erickson said: "go and find your own ways to change".

Ericksonian hypnosis is essentially therapeutic, it is not spectacular. This method can be integrated into the treatment process without significantly increasing the time of the procedure.

Among the different conversational hypnosis techniques that exist, there is the magic pen where the patient is made to choose a pencil, the liquid is described, the colour, the smell... and the pencil is put on the hand, the liquid is allowed to imagine that it is put in the hand and it is spread "like sunshine", the liquid is made to feel by rubbing the hand, which creates a protection.

There is another technique which takes the patient to the place they want with a formal, nonconversational induction, often questioning, but lasting more than thirty minutes.

Each way brings the patient into a similar altered state of consciousness. Everything is improvised, it depends on the individual.

Within the framework of the Hymn project, the "magic glove" technique was chosen because it seems to us to be the simplest to carry out with the patient and is consistent with the hand infiltration technique. This technique consists of creating an imaginary glove, invented by the

patient himself, around his hand which will "anaesthetise" the pain. The patient's hand is cataleptic or levitated, and is then connected to what is pleasant, "luminous".

We wish to evaluate here the interest of hypnosis on the pain felt by the patient during the realization of an echo-guided infiltration of the hand, one of the most painful extremities during infiltrations.

## **1.2. *BENEFITS AND RISKS FOR RESEARCH PARTICIPANTS***

### **1.2.1. *Benefits***

#### **1.2.1.1. *Individual benefit***

The expected benefit of a hypnosis session prior to an ultrasound-guided hand infiltration is a reduction in the sensation of pain at the time of the infiltration.

This benefit will be objectively assessed by means of a pain assessment directly by the person using a pain scale (VAS)

#### **1.2.1.2. *Collective benefit***

The use of hypnosis in the performance of painful treatments such as ultrasound-guided hand infiltration could optimise patient care.

This could also reduce the time of the procedure as patients will be more relaxed and the rheumatologist will be able to perform the procedure more accurately.

### **1.2.2. *Risks***

No excess risk is expected as a result of participation in the study.

#### **1.2.2.1. *Individual risk***

- Related to the hypnosis procedure: no risk has been demonstrated for the practice of hypnosis [2]. No individual risk is expected for this study

#### **1.2.2.2. *Individual constraints***

The constraints related to filling in the questionnaires are considered minimal. In the experimental group "Infiltration under ultrasound + Hypnosis", the consultation will be extended by about ten minutes compared to usual practice.

#### 1.2.2.3. Collective risk

No collective risk is expected for this study. There are no changes in management outside of randomisation.

### 1.2.3. **Benefit/risk balance**

The person in charge of the research qualifies it as **interventional research with minimal risks and constraints**, because the hand infiltration technique and the drugs are used in common practice. It is not expected that there will be any excess risk in relation to these practices as a result of participation in the protocol.

The research does not focus on innovative or obsolete techniques or strategies.

The overall management of the patient will be the same as usual.

Consequently, the particular modalities of implementation in the research represent negligible constraints for the person who lends himself to the research. (Article R 1121-3 of the Public Health Code (CSP), decree n° 2006-477 of 26 April 2006)

The person in charge of the research will therefore, before any implementation of the research, submit the study protocol to a Committee for the Protection of Individuals in accordance with article L 1121-1 of the Public Health Code (CSP) as they result from laws n° 2004-806 of 9 August 2004 and n° 2006-450 of 18 April 2006 relating to public health policy, for a favourable opinion and confirmation of the qualification of the research.

## **2. OBJECTIVES AND JUDGING CRITERIA**

### ***2.1. OBJECTIVE AND PRIMARY ENDPOINT***

#### **2.1.1. *Main objective***

The main objective is to show that the practice of hypnosis makes it possible to reduce the pain felt by the patient during an ultrasound-guided infiltration procedure on the hand.

#### **2.1.2. *Primary endpoint***

VAS pain at rest 5 minutes after the ultrasound-guided infiltration of the hand

## **2.2. OBJECTIVES AND SECONDARY ENDPOINTS**

### **2.2.1. Secondary objective(s)**

Assessment of patient anxiety 5 minutes after the procedure is performed

### **2.2.2. Secondary endpoint(s)**

Spielberger Anxiety-Status Scale (STAI form Y-A) score experienced 5 minutes after infiltration

## **3. STUDY POPULATION**

### **3.1. DESCRIPTION OF THE POPULATION**

**Number of patients to be randomised:** 80 patients randomised (see § justification of the number of subjects).

This study is aimed at adult patients treated in the rheumatology department of the CHD Vendée for the first time for an ultrasound guided infiltration of the hand.

Recruitment will be carried out prospectively on arrival in the rheumatology department

4 to 6 new patients per month are treated by the CHD Vendée for a first hand infiltration under ultrasound.

The study plans to include 92 patients. However, the inclusion period will end when 80 patients are randomised.

### **3.2. INCLUSION CRITERIA**

- Patient with an indication for a first hand infiltration under ultrasound
- Patient of legal age
- Patient with the ability to understand the protocol and who has given informed consent
- Patient with social security coverage

### **3.3. NON-INCLUSION CRITERIA**

- Patient with a preventive pain patch on the area to be infiltrated
- Contraindication to infiltration (unbalanced diabetes, unbalanced hypertension, ongoing infections)
- Hearing impaired patient

- Patient under guardianship/guardianship
- Minor
- Pregnant woman
- Patient participating in another interventional research protocol
- Patient unable to follow the protocol, as judged by the investigator.

**3.4. *EXPECTED DURATION OF PARTICIPATION OF INDIVIDUALS AND A DESCRIPTION OF THE TIMING AND DURATION OF ALL TRIAL PERIODS***

Inclusion period: 26 months

Duration of patient participation: 2 hours

Duration of the study: 26 months

## **4. DESIGN AND STUDY PROCESS**

### ***4.1. GENERAL RESEARCH METHODOLOGY***

The research has the following characteristics:

- Type of research: Minimal Risk Minimal Constraint Interventional Research (MRIC) - Single-centre, controlled, randomised, open-label, superiority study.

### ***4.2. CONDUCT OF THE STUDY AND TIMETABLE OF THE STUDY***

#### **1. Inclusion and Randomisation (D0)**

oIn order to ensure the feasibility of the study, patients scheduled for ultrasound-guided hand infiltration will be scheduled when two nurses, one of whom is trained in hypnosis, are present on the ward.

The inclusion consultation will check the inclusion and non-inclusion criteria. A presentation of the study will be made by one of the two nurses. Written information will be given to the eligible patient. The patient's oral, informed consent will then be collected.

Randomisation will be carried out during this consultation. Depending on the randomisation arm the patient will receive either :

- A single ultrasound-guided infiltration of the hand (standard arm)
- A single ultrasound-guided infiltration of the hand under hypnosis (experimental arm).

In this study, where the standard of care is "infiltration only", a placebo group is not planned. The aim of our study is to evaluate the contribution of hypnosis as a global approach to patient management.

#### **Echo guided infiltration technique - Standard arm:**

The patient will be installed in the usual way by the non-hypnosis trained nurse.

The rheumatologist will carry out the localisations under ultrasound. The nurse will then disinfect the patient's hand in 3 steps with an iodinated skin antiseptic. The infiltration will be carried out in a standardised way by a rheumatologist of the department.

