#### **Hypnosis-guided echo infiltration technique - Experimental arm:**

Hypnosis will be started after the result of the randomisation, the patient will be taken care of by the nurse trained in hypnosis (see § 4.4 description of the method used).

When the patient is ready, just after the hypnosis session, the nurse will disinfect the patient's hand in 3 steps with an iodinated skin antiseptic and the rheumatologist will perform the infiltration in a standardised way.

In both groups, the Spielberger Anxiety-Trait Scale (STAI form Y-B) will be collected before the intervention and before hypnosis (experimental arm). This score will be used to characterise and describe patients' anxiety before the intervention.

In both groups, the Spielberger Anxiety-Status Scale (STAI form Y-A) will be performed 5 minutes after the infiltration procedure.

The pain VAS will be collected before the hypnosis intervention in order to characterise the pain related to the pathology.

[figure not shown]
The pain VAS will then be collected 5 minutes after the infiltration procedure in order to characterise the pain linked to the infiltration procedure.

The use of analgesic treatments by the patient before the ultrasound guided infiltration will be collected.

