#### 4.3. SCHEME OF THE STUDY

#### 4.4. DESCRIPTION AND JUSTIFICATION OF THE METHOD STUDIED

The duration of the hypnosis session will be measured.

The hypnosis session consists of building a "magic glove" with the patient on the hand on which the infiltration will be performed.

The nurse sets up the patient and the rheumatologist uses the ultrasound machine to locate the hand.

The nurse, trained in hypnosis, starts the timer, takes the patient's hand in her hand and begins the hypnosis session. The principle is to get the patient to imagine a glove that they will create to put on their painful hand.

The nurse lets the patient choose the colour, material and asks how far the glove fits on the arm.

The nurse guides the patient to put the glove on each finger by touching the hand.

By suggestion, the nurse forms an anaesthetic area on the hand according to the patient's choice.

If the "protection" is not sufficient, the nurse adds a "strip" or "resin" to increase the anaesthetic.

A phenomenon of catalepsy or levitation of the hand is generated in the patient.

The "magic glove" technique is suitable for hand infiltration because a glove can be slipped onto a hand.

When the patient is ready, the nurse stops the timer and disinfects the patient's hand in 3 steps and the rheumatologist carries out the infiltration in a standardised manner.

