### **6.2.5. Method of accounting for missing, unused or invalid data**

All missing data and the reason for it will be described in each group.

For the analysis of the primary outcome, a multiple imputation method will be applied.

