### **6.2.7. Selection of persons to be included in the analyses**

The main analysis will be performed on the Intent-to-Treat (ITT) population, i.e. on all randomised patients.

A complementary analysis will be performed on the Per Protocol (PP) population including the randomised patients for whom no major protocol deviations have been identified.

A data review meeting will be held to review and define the major criterion or not for each of the deviations.

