### **6.2.8. Randomisation**

Randomisation will not be stratified.

It will be carried out in a 1:1 ratio and will be done in blocks.

Randomisation will be carried out in Ennov Clinical by connecting to the website: <https://www.dirc-hugo-online.org/csonline/>. The connection will be made through a login, a password and a study number, delivered by the data manager of the Research Unit of the La Roche sur Yon Hospital. The following information must be filled in:

- First initial of the name,
- First initial of the first name,
- Month and Year of birth,
- Compliance with inclusion and non-inclusion criteria (yes/no),

Randomisation will be carried out by the investigator after confirmation of the possibility of inclusion in the study. The inclusion number will be assigned automatically during randomisation. A confirmation email will be sent to the person who performed the randomisation and to all persons involved.

The randomisation list will be carried out by the statistician of the Research Unit of the CHD of La Roche sur Yon. An explanatory guide to randomisation will be available online in Ennov Clinical.

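### In the standard arm, ultrasound localisation follows open-label allocation, so the target and any decision not to proceed can be settled with the arm known; randomising after localisation would avoid this

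*Combined protocol and SAP*

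**What the plan says.** **Randomisation.** Section 4.2 (Inclusion and Randomisation, D0) states: "Randomisation will be carried out during this consultation". Section 6.2.8 adds: "Randomisation will be carried out by the investigator after confirmation of the possibility of inclusion in the study". The web form in 6.2.8 asks for initials, month and year of birth, and a yes/no on the entry criteria. It does not ask whether the injection will go ahead. Section 4.1 describes the trial as open-label.

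**Standard arm (4.2).** The order is "The patient will be installed in the usual way by the non-hypnosis trained nurse", then "The rheumatologist will carry out the localisations under ultrasound", then disinfection and injection.

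**Experimental arm.** Section 4.2 says: "Hypnosis will be started after the result of the randomisation". Section 4.4 says: "The nurse sets up the patient and the rheumatologist uses the ultrasound machine to locate the hand". In the next sentence of 4.4 the hypnosis-trained nurse starts the timer.

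**Counting and analysis.** Section 3.1 closes recruitment at 80 randomised. Section 6.2.7: "The main analysis will be performed on the Intent-to-Treat (ITT) population, i.e. on all randomised patients". Section 6.2.5: "For the analysis of the primary outcome, a multiple imputation method will be applied". The primary endpoint in 2.1.2 is a resting pain VAS timed from the injection, so it has no value without one. Section 4.7.1 lists only consent withdrawal as a reason to stop participation early.

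**The concern.** Localisation is described in both arms and comes before hypnosis, so nothing in the plan requires the arm to be known when it is done. As the standard arm is written, however, the arm is known. This has two consequences.

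- **Choice of target.** The rheumatologist may settle where to inject knowing the arm. That could affect procedural pain even if every patient is injected.
- **Patients not injected.** If the injection does not go ahead after allocation, the patient has already used a randomised place and belongs to the ITT set. The only stated treatment of a missing primary outcome is multiple imputation. Pain from an injection that was not given is not an unobserved value in the ordinary sense, because no true value exists. If non-performance differed by arm, the comparison could be biased, and an unspecified imputation model offers no assurance against that.

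**Working it through.** **Step 1: order of events.** For the standard arm, set-up is reserved to the nurse without hypnosis training. A nurse can be chosen by arm only once the arm is known, and localisation follows set-up. Localisation therefore comes after allocation. For the experimental arm, 4.2 ties only the start of hypnosis to the randomisation result. In 4.4 the nurse who does the set-up is not identified, and the hypnosis-trained nurse is named only afterwards, when the timer starts. Localisation before or after allocation is compatible with that text. The scheme in 4.3 is not visible in the copy reviewed.

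**Step 2: the plan's own sample size.** Inputs from 6.2.2: difference δ = 2, SD σ = 3, alpha 5%, power 80%. Allocation is 1:1 (6.2.8) and the test is Student's t (6.2.1). Sidedness is not stated.

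- Normal approximation, two-sided: n per arm = 2(1.96 + 0.8416)² × (3/2)² = 35.3, so 36 per arm and 72 in total.
- Noncentral t, two-sided: n = 36.3, so 37 per arm and 74 in total, which matches the plan. A one-sided test (normal approximation) gives 56 and does not match.
- 74 × 1.05 = 77.7, so 78. The plan's 80 is 80/74 − 1 = 8.1% above 74.
- Margin: 80 − 74 = 6 patients, and 6/80 = 7.5%.

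**Step 3: power when k of 80 have no outcome.** The documents give no rate of injections not performed, so k is an assumed range. Losses are split evenly between arms and imputation is taken to add no information. With n = (80 − k)/2 per arm, the noncentrality is (δ/σ)√(n/2) on 2n − 2 degrees of freedom. For k = 0 this is 0.6667 × √20 = 2.981; for k = 6 it is 0.6667 × √18.5 = 2.867.

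| k | % of 80 | outcomes | power |
|---|---|---|---|
| 0 | 0 | 80 | 83.8% |
| 2 | 2.5 | 78 | 82.8% |
| 4 | 5 | 76 | 81.8% |
| 6 | 7.5 | 74 | 80.8% |
| 8 | 10 | 72 | 79.7% |
| 12 | 15 | 68 | 77.3% |

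**Step 4: a less favourable assumption.** Section 6.2.5 gives no imputation model. If imputed values carried no arm difference (for example, if arm were left out of the model), the effect would be diluted to 2(1 − k/80), with all 80 analysed.

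| k | diluted difference | power |
|---|---|---|
| 4 | 1.90 | 79.9% |
| 6 | 1.85 | 77.8% |
| 8 | 1.80 | 75.5% |
| 12 | 1.70 | 70.6% |

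**Step 5: does another allowance cover these patients?** Section 3.1 plans 92 inclusions for 80 randomised, a gap of 12/92 = 13.0%. That gap lies before randomisation and does not cover losses after it.

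**The case against.** The strongest reply is that localisation is not presented as a decision point. Both descriptions read as guidance for the needle. The patient already has an indication (3.2), has been screened for contraindications (3.3), has been scheduled for the injection (4.2) and is examined at the inclusion visit. A reader might infer that ultrasound regularly shows no suitable target and that such patients accumulate in the ITT set. The documents do not support that: they neither say that localisation can cancel an injection nor give a frequency.

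A reader might also infer that both arms are localised after allocation. The text fixes this only for the standard arm.

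A third tempting reading is that the plan imputes pain for injections never given. Section 6.2.5 does not say so. It states a general rule with no exception and leaves the case open.

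Other points on that side also stand. The additional patients in 6.2.2 are there to protect power, and they cover a modest number of losses. Reordering does not stop a patient declining on learning the arm. Withdrawal is partly provided for: data already collected are kept unless the patient objects (4.7.2), missing data and reasons are described by group (6.2.5), and there is a per-protocol analysis (6.2.7). That analysis is only complementary, however, and which deviations count as major is left to a review meeting.

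Finally, letting either nurse do the set-up could expose control patients to the hypnosis-trained nurse. This matters because 1.1 treats explanation and relaxed discussion as a form of conversational hypnosis. The risk is avoided if the other nurse does set-up in both arms.

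None of this supplies a reason to know the arm before localisation.

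**Conclusion.** The point holds in limited form. In the standard arm as written, localisation follows open-label allocation; in the experimental arm the order is unclear. The target, and any decision not to proceed, can therefore be settled with the arm known. A randomised patient who is not injected counts towards the 80 and falls in the ITT set with no specific handling rule.

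Power is a minor issue. Up to 6 of 80 such losses leave 80.8%, and 8 leave 79.7%, assuming the plan's δ and σ, even losses and imputation that adds no information. Under the dilution assumption power is just below 80% at 4 losses, but that rests on an imputation model the plan does not describe. The 6-patient margin must also serve every other loss after randomisation.

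A reader might conclude that the trial is underpowered or its comparison biased. The documents do not support either conclusion: no rate of non-performance is given, and bias would require the choice of target or non-performance to depend on arm. The case for change is that it is nearly free. It conceals allocation while these decisions are made and reduces the number of randomised patients with no possible outcome. The change is recommended, not essential.

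**What to change.** In 4.2, 4.4 and 6.2.8, state one order for both arms:

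1. Consent and check of entry criteria.
2. Baseline pain VAS and STAI-trait.
3. Set-up by the non-hypnosis-trained nurse in both arms, then ultrasound localisation.
4. The rheumatologist confirms that the injection will go ahead, recorded as a yes/no item on the randomisation form.
5. Randomisation.
6. Hypnosis (experimental arm) or disinfection (standard arm).

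A patient with a no at step 4 is counted as included but not randomised and does not use one of the 80 places. If the scheme in 4.3 already shows localisation first, only the wording needs aligning.

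**Cost:** a wording change and one form field, with no new procedure or extra patients. The team waits briefly for the web allocation, and the experimental arm has a nurse handover after set-up.

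**What it leaves open:** patients who withdraw after learning their arm remain in the ITT set. They need a separate sentence in 6.2.5 or 6.2.7 saying how randomised but non-injected patients are analysed, with the imputation model specified and arm included in it.
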